Patients with histologically proven small cell lung cancer who have undergone at least four cycles of first-line chemotherapy with a partial or complete response, above 22 years of age, no evidence of intracranial metastasis.

g) Materials That Will Be in Contact with Tissues

The INE transducer arrays are applied directly to the skin.

These arrays are sterile single use devices and incorporate the following:

Part Name	Functions
1 Cover tape	Provides adhesion of the array to patients' skin
2 INE transducer array	The array delivers the treatment to the patient and measures the temperature
3 Conductive gel layers and Ceramic discs (beneath)	Gel: Ensures electric contact between the transducer array and the skin Ceramic disc: Used for the TTFields transmission
4 Mid-pads	Mechanically stabilizes the gel over the array
5 Overlapping liner	Covers the gel and the cover tape
6 Applied part cable with black connector or white connector	Connects the transducer array to the connection box

h) Training and Specific Medical or Surgical Procedures Involved in the Use of the Investigational Device

The NovoTTF-200A System is easy to use and a simple training by the Device Support Specialist (DSS) is sufficient for patients and the study team to apply the investigational device according to its intended use. No specific medical/surgical procedures are needed for the use of the investigational device.

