TTFields are a non-invasive, regional antimetabolic treatment modality with minimal toxicity which have been approved for the treatment of recurrent and newly diagnosed glioblastoma (GBM) by the Food and Drug Administration (FDA) in the United States and have obtained a CE mark in Europe for the same indications. TTFields act by delivering low intensity (1-3 V/cm), intermediate frequency (100-300 kHz), alternating electric fields to the tumor using non-invasive transducer arrays placed on the skin around the region of the body containing the tumor. TTFields act predominantly during two phases of mitosis: 1) during metaphase, by disrupting the formation of the mitotic spindle, and 2) during cytokinesis, by dielectrophoretic dislocation of intracellular constituents resulting in apoptosis [10], [11]. The efficacy of TTFields is frequency dependent on specific cell types. The anti-mitotic effect of TTFields has been shown in multiple cell lines when the appropriate frequency was utilized. This includes primary brain tumor cell lines and cell lines from other tumors which commonly metastasize to the brain (glioblastoma at 200 kHz [12], NSCLC at 150kHz [13], breast carcinoma at 120kHz [14], and melanoma at 100kHz [10]). For SCLC, maximal cell death has been found to occur at 200 kHz [15].

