4. RISKS AND BENEFITS OF THE INVESTIGATIONAL DEVICE AND CLINICAL INVESTIGATION

The risks associated with use of the NovoTTF-200A are the same as those associated with use of the approved Optune System. Principally, the risks are electrical or mechanical failure leading to electrical shock or electromagnetic interference, as well as the risk that the treatment will not be effective in delaying tumor progression or causing regression. Additional risks include skin irritation, and skin breakdown or infection at electrode sites. Other risks include headaches, fatigue, falls, and muscle twitching. Technical failure is extremely unlikely due to stringent compliance with all standard design and manufacturing safety protocols. In addition, appropriate measures have been taken to minimize the risk to study subjects, including preclinical *in vitro* and *in vivo* testing to ensure safe operation of the device.

Approximately 25 patients will be enrolled in the proposed study and will receive Novo-TTFA treatment. Participants are considered enrolled after their eligibility is confirmed and the coordinating center sends the enrollment confirmation to the site. Considering the minimal toxicity and promising efficacy seen in the GBM studies, the number of patients exposed to this treatment in the proposed study and the risks associated with the alternative treatments for these patients, the company believes that the possible benefits of NovoTTF-200A treatment clearly exceed its potential risks.

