 - c. History of cerebrovascular accident (CVA) within 6 months prior to start of study treatment
 - d. Active infection or serious underlying medical condition that would impair the ability of the patient to received protocol therapy.
 - e. History of any psychiatric condition that might impair patient's ability to understand or comply with the requirements of the study or to provide consent.
4. Active implantable electronic medical devices in the brain; a skull defect, a shunt, or bullet fragments
 5. Known allergies to medical adhesives or hydrogel
 6. Unable to operate the NovoTTF-200A device independently or with the help of a caregiver
 7. If a female, currently pregnant, breastfeeding, or unwilling to avoid pregnancy while on study treatment.
 8. Concurrent brain directed therapy (beyond NovoTTF-200A as per protocol)
 9. Prior clinical trial participation with brain directed therapy
 10. Concurrent treatment clinical trials

4. Criteria for Removal from Study Therapy

Criteria for removal from study therapy include:

1. Patient request – The patient may withdraw from the study at any time.
2. Lack of compliance – The Sponsor or investigator may remove a patient from the study for lack of compliance to the study protocol.
3. Intolerable toxicity - Patients may be removed from study treatment for intolerable adverse events attributable to the device. Any serious adverse event deemed life threatening by the treating physician that is definitely related to the study device will be cause for immediate cessation of treatment.
4. Intracranial failure – As defined in section 9(a) of the protocol
5. Death

5. Enrollment Plan

a) Start Date of Enrollment

Enrollment of the first patient is expected during the second quarter of 2017.-

b) Total Expected Duration of the Clinical Investigation

The study is expected to last for 36 months.

c) Expected Duration of Each Subject's Participation

Subject participation in the trial is anticipated to be 10-15 months.

d) Number of Subjects Required to be Included in the Clinical Investigation

A total of 25 patients will be accrued for this study at up to three institutions. Any patients deemed screen failures may be replaced with a new patient.

e) Estimated Time Needed to Select this Number (i.e., Enrollment Period).

It is assumed that the accrual will take place over 24 months.

Enrollment Procedures

Guidelines for VICC and Participating Institutions

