16. ADVERSE EVENTS, ADVERSE DEVICE EFFECTS AND DEVICE DEFICIENCIES

As defined by MEDDEV 2.7/3 Revision 3 (May 2015), an adverse event is any untoward medical occurrence, unintended disease or injury or any untoward clinical signs (including an abnormal laboratory finding) in subjects, users or other persons whether or not related to the investigational medical device. This includes events related to the investigational device or the comparator, events related to the procedures involved (any procedure in the clinical investigation plan). For users or other persons, this is restricted to events related to the investigational medical device.

1. Possible Adverse Events

a) NovoTTF-200A System (200 kHz TTFIELDS)

In the phase III trial in patients with recurrent GBM, device-related adverse events (grade 1/2) included: medical device site reaction (skin reaction) 16%, headache 3%, malaise 2%, muscle twitching 1%, fall 1% and skin ulcer 1%. There were no serious adverse events attributed to the device. Long-term use of TTFIELDS from EF-14 trial was associated with localized skin toxicity: Mild to moderate skin irritation was observed in 43% of patients treated with TTFIELDS plus temozolomide and severe skin reaction (grade 3) in 2%. Mild anxiety, confusion, insomnia, and headaches were reported more frequently in the patients treated with TTFIELDS plus temozolomide and occurred mainly at the time of therapy initiation.

Treatment with NovoTTF-200A is not expected to cause any serious side effects. However, it is possible that investigational treatment may cause any of the following:

1. Local heat and tingling "electric" sensation beneath the transducer array
2. Allergic reaction to the adhesive or to the gel
3. Skin irritation or skin breakdown
4. Infection at the sites of transducer array contact with the skin

5. Open sores, ulceration or blisters underneath transducer arrays
6. Headache
7. Fatigue
8. Falls
9. Muscle twitching
10. Electrical or mechanical failure leading to shock

b) Systemic Chemotherapy / Therapy

Patients receiving chemotherapy or biologic agents for their systemic disease are expected to experience adverse events as listed in the package insert for each agent given.

c) Supportive Medications

Supportive medications may be administered at the discretion of the investigator.

2. Adverse Event Collection and Reporting

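### Exclusion 4 bars active electronic implants only when they lie in the brain, so one under the scalp or in the skull is not expressly excluded

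*Combined protocol and SAP*

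**What the plan says.** Section 6, item 3 (Subjects), exclusion 4: "Active implantable electronic medical devices in the brain; a skull defect, a shunt, or bullet fragments".

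On where the arrays go, Section 2(g) states "The INE transducer arrays are applied directly to the skin". Section 3(b) describes the treatment as delivering "alternating electric fields to the tumor using non-invasive transducer arrays placed on the skin around the region of the body containing the tumor". Section 6, item 6(a), has every patient's head shaved before the arrays are placed from an individually planned layout.

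On exposure, the same item fixes the output at 200 kHz in two perpendicular directions, up to 707 mA RMS. It requires average wear of 18 hours or more per day, and it does not allow investigators, patients or caregivers to alter the device.

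**The concern.** The plan treats an active implant inside the treated organ as a reason not to treat. The field reaches that organ only by crossing scalp and skull, so an active device in either layer is nearer the arrays than the device that is barred. As written, the rule excludes the more distant implant and is silent on the nearer one.

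At stake is the safety of an individual carrier, should one present. Because the output cannot be lowered for a particular patient, screening is the point at which exposure can be avoided altogether. The primary endpoint, the secondary analyses and the sample size of 25 are untouched.

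**Working it through.** The plan gives no figure to reproduce and no sample-size or error-rate arithmetic applies. The check is a comparison of the text.

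1. **Which criteria name an implant.** The five inclusion criteria cover age, life expectancy, disease and response, performance status and laboratory values. The ten exclusions cover brain metastases, prior malignancy, comorbidities (3a to 3e), the items in exclusion 4, adhesive or gel allergy, ability to operate the device, pregnancy and breastfeeding, concurrent brain-directed therapy, earlier trials of such therapy, and concurrent treatment trials. Only exclusion 4 mentions electronic devices.

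2. **How exclusion 4 is built.** It has four items. The location limit is attached to the first, the active implant. A skull defect is by definition outside the brain, and the shunt and the fragments carry no stated location. The criterion therefore already looks beyond the brain for bone and for passive objects, but not for active electronics.

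3. **Where the field passes.** Arrays on the skin (Section 2(g)) of a shaved head (Section 6, item 6(a)), with the brain as target, place scalp and skull between source and target.

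4. **How long.** A mean of 18 hours a day is 18/24 = 75% of the day, continued until intracranial failure, death or unacceptable side effects. Arrays move by about 2 cm at each replacement and then back. No instruction tells the planner to avoid an implant.

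5. **What else might stop a carrier before exposure.**
   - Exclusion 3d, "Active infection or serious underlying medical condition that would impair the ability of the patient to received protocol therapy", allows an investigator to refuse, but it turns on judgement about a medical condition and does not mention devices.
   - Baseline medical history, physical examination and neurological examination (Section 7(a)) could reveal an implant. No listed criterion then says what to do about one outside the brain.
   - Central review (Section 6, item 5) checks source records against the eligibility checklist. The checklist is not among the documents, so any extra wording in it cannot be confirmed.
   - Array planning happens patient by patient and might bring an implant to light, but it is not an eligibility step.
   - The 3T brain MRI at baseline and every 8 weeks keeps out anyone whose implant cannot enter the scanner. It is done with the system removed, so passing it says nothing about compatibility with daily 200 kHz fields.

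6. **What acts after exposure.** Section 6, item 4, provides that "Patients may be removed from study treatment for intolerable adverse events attributable to the device". Breaks of up to 3 weeks are allowed for device-related events, and Section 16.2(e) halts enrolment after more than one unanticipated serious device effect. Each requires that something has already happened.

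Steps 1 to 3 establish the gap in wording. Steps 5 and 6 show that it is narrowed but not expressly closed.

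**The case against.** The strongest reply is that the documents show no hazard to such an implant. Section 4 says "Principally, the risks are electrical or mechanical failure leading to electrical shock or electromagnetic interference", which ties interference to a fault, and adds "Technical failure is extremely unlikely due to stringent compliance with all standard design and manufacturing safety protocols". A reader might take interference to be a listed risk of ordinary use. The text does not support that. Section 16.1(a) mentions warmth and tingling under an array, but these are sensations in skin and are not evidence about electronics. This part of the reply stands: harm in normal operation is an inference, drawn from the plan's own decision to exclude active implants in the brain.

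A second reply is that the screens are better than the wording suggests. History, examinations, individual planning and repeated MRI all make it less likely that a carrier enrols unnoticed, and a device set into bone might be read as a skull defect, a term the plan leaves undefined. This too stands as far as it goes. It lowers the chance of the problem without supplying an express bar, and an arguable reading of an undefined term is a weak safeguard.

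A third reply concerns reach. A reader might extend the point to implants in the neck or the trunk. No section places arrays or field in the neck, and the argument from the path of the field stops at the head. Exclusion 3b would remove some patients with cardiac rhythm devices because of the arrhythmia, not the implant. The documents do not settle either region.

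**Conclusion.** The gap in wording is real and confined to the head outside the brain: an active implant under the scalp or in the skull is not expressly excluded. It merits consideration as a minor safety clarification. Confidence that it would matter in practice is low.

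The conclusion rests on two things: the eligibility list in Section 6 is complete as printed, and the reason for barring implants in the brain applies equally to layers that the same field crosses. The documents offer no reason for the narrower wording. Section 4 equates the risks with those of the approved system, but that system's labelling and any interference data are not among the documents.

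A reader might want the chance of enrolling or harming a carrier among the 25 patients. The documents contain neither prevalence nor interference data, so any such figure would merely reflect the value assumed. Most likely no patient is affected.

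**What to change.** In exclusion 4, replace the first item with *active implanted electronic medical devices in the head (brain, skull or scalp)*, leave the other three items as they are, and change the matching line of the eligibility checklist. Alternatively, the sponsor could state why an active implant outside the brain is acceptable under the arrays. Whether to go further, to the neck or the rest of the body, is a sponsor decision.

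The cost is one protocol line and one checklist entry. The only downside is the possible loss of a rare candidate, and Section 6, item 5(d), already allows screen failures to be replaced.

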1. WBRT
2. Best supportive care

7. PATIENT EVALUATIONS AND FOLLOW UP PLAN

A table of the study procedure calendar for this study is provided in **Appendix C**.

a) Pre-treatment Evaluation (Baseline)

The following will be performed within 21 days prior to registration (start of study treatment with the NovoTTF-200A System):

1. Verify informed consent is signed
2. A high resolution, isovolumetric T1-weighted post-gadolinium MRI of the brain using a 3T MR scanner. **Treatment with the NovoTTF-200A System is to begin no later than 21 days after the baseline MRI.** Additional parameters include:
 - a) FOV: 256 mm x 256 mm

- b) Matrix: 256x256
- c) Slice thickness: 1 mm
- d) Full brain coverage

The same slice thickness and contrast material type & dose should be maintained throughout the entire study. The NovoTTF-200A System and all components including the transducer arrays must be removed and cannot be brought into the MR environment.

- 3. Medical history
- 4. Concomitant medications
- 5. Karnofsky Performance Status (KPS) score recording
- 6. Physical examination and vital signs
- 7. Neurological examination
- 8. Neurocognitive testing: Hopkins Verbal Learning Test (HVLT-R) for free recall, delayed recall and delayed recognition, Controlled Oral Word Association Test (COWAT); and Trail Making Tests (TMT) Parts A and B
- 9. Quality of Life questionnaire (EORTC QLQ C30 with BN20 addendum)
- 10. Serum Pregnancy test (if applicable) within 14 days
- 11. Complete blood count including differential
- 12. Serum chemistry panel, including:
 - 1. BUN, Creatinine
 - 2. Sodium, Potassium
 - 3. ALT, AST, Bilirubin
- 13. Coagulation tests (PT, PTT)

b) Follow-up until Intracranial Failure

Once every 8 weeks until intracranial failure the following examinations will be performed:

- 1. Physical examination and vital signs
- 2. KPS score recording
- 3. Neurological examination
- 4. Complete blood count including differential
- 5. Serum chemistry panel, including:
 - 1. BUN, Creatinine
 - 2. Sodium, Potassium
 - 3. ALT, AST, Bilirubin
- 6. Coagulation tests (PT, PTT) as clinically indicated
- 7. Adverse event collection and recording
- 8. Concomitant medication recording
- 9. A high resolution, isovolumetric T1-weighted post-gadolinium MRI of the brain using a 3T MR scanner. Additional parameters include:
 - a) FOV: 256 mm x 256 mm
 - b) Matrix: 256x256
 - c) Slice thickness: 1 mm
 - d) Full brain coverage

The same slice thickness and contrast material type & dose should be maintained throughout the entire study. The NovoTTF-200A System and all components including the transducer arrays must be removed and cannot be brought into the MR environment.

- 10. Device compliance (if applicable)

Once every 8 weeks, for one year or until intracranial failure (whichever comes first) the following

neurocognitive tests will be performed:

1. HVLt-R
2. TMT Part A and B
3. COWAT

Once every 8 weeks, for one year or until intracranial failure (whichever comes first) the following Quality of Life questionnaires will be performed:

1. EORTC QLQ C30
2. EORTC BN20 addendum

c) Follow up 8 weeks from treatment termination

1. KPS score recording
2. Physical examination and vital signs
3. Neurological examination
4. Complete blood count including differential
5. Serum chemistry panel, including:
 1. BUN, Creatinine
 2. Sodium, Potassium
 3. ALT, AST, Bilirubin
6. Adverse event collection and recording
7. Concomitant medication recording
8. A high resolution, isovolumetric T1-weighted post-gadolinium MRI of the brain using a 3T MR scanner. Additional parameters include:
 - a) FOV: 256 mm x 256 mm
 - b) Matrix: 256x256
 - c) Slice thickness: 1 mm
 - d) Full brain coverage

The same slice thickness and contrast material type & dose should be maintained throughout the entire study. The NovoTTF-200A System and all components including the transducer arrays must be removed and cannot be brought into the MR environment.

Please see **Section 9.a** and **Appendix B** for details about the neurocognitive function assessments.

Following Study Treatment Discontinuation

Patients will have additional follow-up outside of scheduled study follow-up at the discretion of the treating physician.

Post Intracranial Failure Follow-up

Following intracranial failure, patients will be followed every 4 weeks for survival (this can include telephone call follow-up and does not require a clinical visit). Patient death date will be captured in the CRFs.

Foreseeable Factors That May Compromise the Outcome of the Clinical Investigation or the Interpretation of Results

There are no foreseeable factors that may compromise the outcome of the clinical investigation or the interpretation of the study results.

8. MONITORING PLAN

Study monitoring will be performed by the coordinating center assigned this responsibility by the Sponsor. Study monitoring functions will be in compliance with recognized Good Clinical Practices, EN-ISO-14155, FDA's IDE guidance documents, and as outlined in 21 C.F.R. § 812.43(d) and 21 C.F.R. § 812.46. The principal function of the clinical monitor is to observe and assess the quality of the clinical study. The monitor's duties include: remote monitoring of study documents and results. The coordinating center will operate under written procedures to ensure compliance with the protocol.

Remote monitoring will take place every 8-16 weeks during the course of the study (as long as there are patients in follow up at the site), and final remote monitoring at the close of the study.

Remote monitoring during the study is intended to assess Investigators' adherence to the Investigational Plan, maintenance of records, reports and investigational devices, and review of source documents for accuracy, completeness, and legibility. The monitor is required to assess the progress of the study toward meeting study objectives, and to identify any concerns that stem from observations of device performance and/or review of the Investigator's patient records, study management documents, and informed consent documents, and to ensure accountability of all patients that have been treated under the study.

The remote monitoring at completion of the study is intended to assure that all the data have been properly completed. Monitoring reports should include resolution of concerns, completion of appropriate follow-up activities, completion of assigned tasks, and any necessary corrective actions. At the close of the study, the monitor will prepare a final report.

The Vanderbilt-Ingram Cancer Center (VICC) oversees patient safety and data monitoring for its investigator-initiated and NIH-NCI funded clinical trials through its Data and Safety Monitoring Committee (DSMC). The purpose of the DSMC is to ensure the efficient implementation and management of VICC Data and Safety Monitoring Plan (DSMP). The Committee maintains authority to intervene in the conduct of studies as necessary to ensure clinical research performed at VICC achieves the highest quality standards.

The VICC DSMC meets on a quarterly basis and ad hoc to discuss data and safety monitoring of clinical trials and to oversee the VICC DSMP. Internal audits for compliance with adverse event reporting, regulatory and study requirements, and data accuracy and completion are conducted according to the VICC DSMP according to study phase and risk. The committee reviews all serious adverse events (SAE) on Vanderbilt sponsored investigator-initiated studies on a quarterly basis and provides DSMC SAE review reports to the Vanderbilt IRB.

